- **iv. Power**
- Sample Size: Each of the 4 sites will recruit 38 infants (total $N=152$) to retain 35 infants for a total of $N = 140$ infants in the study. The initial ($N=152$) and retained ($N=140$, $n=70$ per condition) sample sizes were chosen according to feasibility of recruitment in each site as well as considerations of time and resources needed for a 4-year study.
- Power analysis for Primary Hypotheses 1 & 2: We used a simulation-based power analysis (Muthén & Muthén, 2002; Theommes et al, 2010) to estimate the power for the randomized trial with repeated measures design as evaluated with the proposed Linear mixed modeling (LMM; Laird & Ware, 1982; Wallace & Green, 2002) utilizing FIML for attrition-based missing data. *Mplus* was used for simulations and empirical analyses. Simulations were based on detecting significance in the treatment by time interaction during the intervention phase, γ_{11} . The analysis assumed a small intraclass correlation for the slope across infants (e.g., small variance of the treatment effect of 0.05; Raudenbush & Liu, 2000), a two-tailed nominal error rate of $\alpha = .05$, an initial sample size of 152 infants at baseline, and an attrition scenario of 10% loss by the end of the 3-month intervention (based on patterns observed in previous research conducted by the collaborative team). We conducted the power analysis essentially in support of Hypothesis 1 (the short-term effect at the end of the intervention phase) based on the position that Hypothesis 2 will be supported if the initial effect is then at least sustained through the follow-up period which would be evidenced by a non-significant γ_{21} parameter (no differential change). Prior published research by [name] et al. (2010) and Heathcock et al. (2008) were used to derive effect size estimates for sitting (GMFM, $d=1.21$) and reaching (toy contacts, $d=1.32$), respectively. Pilot data from [name] & [name] and [name] were used to derive

effect size estimates for global development (Bayley III, $d=0.43$) and problem solving (IGDI, $d=1.11$), respectively.

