- Based on our previously stated assumptions and the cited pilot data and prior research, power analyses suggest that the targeted sample size will be sufficient to detect the reported effects with greater than 80% power for three of the four primary outcomes. With $N=152$ initial participants, power to detect mean group differences in slopes during the intervention period is >99% for sitting, 93% for reaching, and >99% for problem solving. As these three outcomes are estimated to be over-powered based on pilot/cited data, given the projected initial sample size of $N=152$ we would be able to detect effect sizes as small as $d=0.48$ for sitting, $d=0.66$ for reaching, and $d=0.56$ for problem solving. Based on the effect size derived from pilot data, power to detect mean group differences in global development improvement during the intervention period at the $d=0.43$ level is only 48%; however, given the projected sample size, we would be able to detect an effect size of $d=0.64$ with 80% power.
- *Power analysis for Primary Hypotheses 3 & 4:* Continuing to use the variability and mean differences from the cited prior research and pilot data as estimates of paths A and D in Figure 2, we conducted an empirical power analysis based on the SEM model presented in Figure 2 using an initial sample size of $N = 152$ infants, and assuming a moderate correlation between the measures at baseline ($r = .32$, explained variance = 10%). With these assumptions, we will have 80% power to be able to support the hypotheses of partial mediation of intervention-driven change over time in global development by intervention-driven changes in sitting and reaching and problem solving if the standardized parameter estimate of the mediator(s) on change in global development (paths B (Hyp. 3) or $C_1 * C_2$ (Hyp. 4) in Figure 2) is at least $\beta=.237$, which corresponds to a medium effect.

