- A complementary power analysis perspective for evaluating Hypotheses 3 and 4 follows MacCallum et al.'s (1996) guidelines for determining adequacy to test the fit of a model, which indicates whether the necessary parameters/effects are being considered. Evaluation of model fit is a prerequisite for evaluating parameters within the model itself. Accordingly, a hypothesis of *close model fit* can be tested by assuming the Type I error rate to be 0.05, a $RMSEA \leq 0.05$ as indicative of *close fit*, and a $RMSEA > 0.10$ as indicative of poor fit. Given the proposed model in Hypothesis 3, $df_{min}=51$, $N=152$, $RMSEA_{null}=0.05$, $RMSEA_{alt}=0.10$, and $\alpha=0.05$, the power to detect close model fit for Hypothesis 3 is >.99. Given the proposed model in Hypothesis 4, $df_{min}=115$, $N=152$, $RMSEA_{null}=0.05$, $RMSEA_{alt}=0.10$, and $\alpha=0.05$, the power to detect close model fit for Hypothesis 4 is .96.
- In summary, the initial sample size of $N=152$ and retained sample size of $N=140$ (70 per group) is appropriate for the study and will likely yield power to test each primary hypothesis at a medium effect size or larger at the $p < .05$ level, with a power of at least .80. The structure of this proposal ensures that we can realistically produce the first randomized efficacy trial of sitting and reaching with young infants within the funding period.

v. Measures [Outcomes]

Rationale for using multiple measures of developmental skills

The use of standardized tests in isolation is not optimal for infants with neuromotor disorders because of the large increments of change in observable motor skills needed to change the score on any one item, and the complexity of child behavior. Furthermore, our research has shown that standardized assessments like the Bayley III focusing on the discrete performance of tasks are not consistent for identifying and classifying delays in the first two years of life and are poorer predictors of future cognition relative to assessments that involve perceptual-motor

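### The 80% mediation threshold of .237 fits a single path but not the product C1×C2, and the closing claim of .80 power at a medium effect contradicts the SAP's own detectable effects

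*SAP*

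**What the plan says.** In SAP section iv, the paragraph on Primary Hypotheses 3 & 4 describes a power analysis "using an initial sample size of $N = 152$ infants". It takes the variability and "mean differences from the cited prior research and pilot data as estimates of paths A and D". It then says "we will have 80% power to be able to support the hypotheses of partial mediation", provided that the standardized effect of the mediator(s) on change in global development "is at least $\beta=.237$, which corresponds to a medium effect". That one condition covers path B (Hypothesis 3) and the product C1×C2 (Hypothesis 4). Section ix confirms that Hypothesis 4 is judged through the indirect effect A×C1×C2.

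The paragraph on Primary Hypotheses 1 & 2 gives detectable effects of d = .48 (sitting), .66 (reaching) and .56 (problem solving). For the Bayley III it gives 48% power at d = .43 and 80% at d = .64. The section closes by saying that the sample size "will likely yield power to test each primary hypothesis at a medium effect size or larger", with power of at least .80.

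**The concern.** A standardized path and a product of two standardized paths are on different scales. A value that is medium for one path is very large for a product, so one number cannot serve both with the same label and the same power. The SAP gives no separate values for C1 and C2, so a reader cannot tell what size of problem-solving route the trial could detect.

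The closing sentence is a second problem and does not depend on the first. It promises .80 at a medium effect for every primary hypothesis, although the same section needs effects of d = .56 to .66 for three of the four outcomes.

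Mediation, the Bayley III and reaching are all primary. If one of them gave a null result, readers would rely on this assurance to treat the trial as adequately powered for it.

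**Working it through.** **Inputs (SAP section iv).** Alpha: "a two-tailed nominal error rate of $\alpha = .05", stated for Hypotheses 1 & 2 and assumed here to carry over to mediation. Initial N is 152. Attrition: "an attrition scenario of 10% loss by the end of the 3-month intervention", so 152 × .9 = about 137. The recruitment plan is "to retain 35 infants for a total of $N = 140$ infants in the study". The SAP's Mplus simulation cannot be rerun, because Figure 2 is not shown and the variances are not given. The checks below use observed variables.

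**1. Reproduce .237 as a single path.** Power = Φ(atanh(b)·√(N−3) − 1.96), with atanh(.237) = .2416.
- N = 137: .2416 × 11.58 − 1.96 = .84, power .799
- N = 140: .2416 × 11.70 − 1.96 = .87, power .807
- N = 152: .2416 × 12.21 − 1.96 = .99, power .839

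So .237 is the 80% detectable size for one path at about N = 137.

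**2. Apply .237 to each of two paths.** The product is .237² = .056. Joint power for C1 and C2 is the square of the single-path power: .64 (N = 137), .65 (N = 140) and .70 (N = 152). An ordinary-regression simulation of treatment → motor skill → problem solving → global development (3,000 replicates, A at d = 1.21, D at d = .43) gives .52 (N = 137) to .58 (N = 152). It is lower because treatment and the mediators are correlated.

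**3. Apply .237 to the product.** Equal paths must be √.237 = .487 each, with joint power above .99. Unequal splits with C1 from .3 to .9 give .88 to above .99.

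**4. Other path sizes.** At an assumed .30 per path, the product is .09. Joint power is .90 to .93 by formula and .80 to .85 in the simulation. By formula, joint power of .80 needs equal paths of about .26 (N = 152) to .27 (N = 137), a product of about .066 to .073.

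**5. The closing summary.** Treat each detectable effect (MDE) as an 80% figure, so that power at d is Φ(2.80·d/MDE − 1.96). Check on the Bayley III: 2.80 × .43/.64 − 1.96 = −.08, power .47, close to the stated 48%. At an assumed medium d = .5:
- Sitting: 1.40/.48 − 1.96 = .96, power .83
- Problem solving: 1.40/.56 − 1.96 = .54, power .71
- Bayley III: 1.40/.64 − 1.96 = .23, power .59

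As the assumed effect runs from d = .43 to .64, Bayley power runs from about .47 to .80. Any definition of medium below .64 therefore falls short for that outcome.

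**6. Reaching.** Power of 93% at d = 1.32 implies SE = 1.32/(1.96 + 1.476) = .384 and an 80% detectable effect of 2.80 × .384 = 1.08. The stated .66 would instead imply power of Φ(2.80 × 1.32/.66 − 1.96) = Φ(3.64), above .999, at d = 1.32. Power at d = .5 is .56 from one figure and about .26 from the other, so no single value can be given.

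**The case against.** Several points on the other side have force.

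- **A reader might infer that the SAP overstates power for Hypothesis 4.** The text does not support that. It claims 80% for a product of at least .237, and at that size power for the indirect effect is .88 or more, so the literal claim is conservative. The .52 to .70 range belongs to a per-path reading that the SAP never states.
- **A reader might infer that the product argument alone refutes the closing summary.** It does not. Medium is undefined in the documents, and at .30 per path power is about .80 to .93. The summary fails on the Hypothesis 1 & 2 detectable effects instead.
- **A reader might infer that the pilot Bayley difference, entered as the direct path D, inflates the simulated total effect by a known amount.** A difference between arms is normally a total effect, so the question is fair. But what was simulated as D cannot be checked. The Figure 2 note labels paths A, C, B1 and B2, which does not match the text. The pilot d = .43 is used for change during the intervention, whereas the mediation outcome runs to one year. No size can be attached.
- **The facts are largely disclosed.** Section iv reports the 48% and the detectable effects openly, and its summary is hedged. It attaches 80% explicitly only to the Bayley's .64; for the other outcomes that reading is an inference. The disclosure limits the harm but does not reconcile the summary with the figures above it.

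One caveat runs the other way. Section ix also expects D to stay significant. In the simplified simulation, adding that condition lowers power to .32 to .36 at .237 per path and to .69 to .72 at a product of .237. Because this depends on the unverified D, it is not counted here.

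**Conclusion.** The stated power figures are wrong as written, in two places.

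First, .237 with 80% power and a medium label suits one path and is mis-specified for C1×C2. As a product it needs about .49 per path, roughly twice the size called medium for B, and has power well above .80. As a per-path value it gives a product of .056 and power of about .52 to .70. No reading yields 80% at a medium effect with this number. The error lies in the detectable size and its label; inadequate power for mediation is not demonstrated. This rests on a simplified observed-variable model with equal or stated path splits, two-sided .05, and path A treated as almost certain to be detected.

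Second, the assurance of .80 at a medium effect for each primary hypothesis contradicts the section's own detectable effects. At an assumed d = .5, power is about .71 for problem solving and .59 for the Bayley III; only sitting (.83) meets it. The reaching figures are mutually inconsistent (80% detectable effect of .66 as stated, against about 1.08 implied by 93% at d = 1.32).

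**What to change.** - Rerun or restate the mediation power with separate values for B, C1 and C2. Report the path sizes that give 80% for A×B and for A×C1×C2 separately, and drop the medium label for the product.
- State whether D was set as a direct or a total effect. If the pilot difference is a total effect, set D net of the indirect effect.
- Reconcile the two reaching figures before reusing either.
- Replace the closing summary with outcome-specific detectable effects and the corrected mediation thresholds.
- Align the numbering and path labels. The problem-solving mediation hypothesis is Hypothesis 3 in section ii, which lists no Hypothesis 4, but Hypothesis 4 in sections iv and ix. The Figure 2 note should use the same path names as the text.

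The cost is one rerun of an existing simulation and a few sentences. Some stated figures will look less favourable. Sample size, models and error control do not change.

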A parallel process growth modeling approach as implemented in the SEM framework will be used to simultaneously address the remaining primary research hypotheses: (3) improvements in sitting and reaching as a function of the intervention will be associated with increases in global development at the end of the project (long term effect); and (4) improvements in global development will be (at least) partially mediated by improvements in problem solving as a function of the intervention at the end of the project (long-term effect). Because the global development and problem solving constructs occur over time and are characterized as improvements (i.e. changes), we consider the mediational model as a SEM (see simplified model in Figure 1) that allows multiple simultaneous direct and indirect paths while modeling growth (Cheong, 2003). This approach will allow us to assess possible mediating effects of improvements in sitting, reaching, and problem solving through the intervention period (RX) on the relationship between intervention participation (START-Play) and improvements in global development through the one-year follow-up (LT). This model will be evaluated for the significance and directionality of included path coefficients and overall model fit. It is expected that the indirect effect of the intervention (derived by tracing solid paths $A*B$, and $A*C_1*C_2$) on child outcomes will be statistically significant and the direct effects of the intervention (dashed path D) will also remain significant, thus demonstrating partial mediation. Hypothesis 3 will be evaluated by comparing the magnitude of the $A*B$ indirect effect to the direct effect, D. Hypothesis 4 will be evaluated by comparing the magnitude of the $A*C_1*C_2$ indirect effect to the direct effect, D. Partial mediation is an appropriate hypothesis as the intervention is expected to have a substantial effect on problem solving, but there are other factors beyond problem solving, sitting and reaching that contribute to improvements in global development that are represented by the direct effect. By hypothesizing that assignment to condition (START-Play) leads to proximal changes in the mediator(s) (RX) which then lead to distal effects in the outcome (LT), we also meet the requirement of temporal precedence necessary for strong mediational inferences.

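### The SAP's power to detect close model fit is really power to reject it; power to show RMSEA below .05 at N=152 is at most about .48 (df 51) and .79 (df 115)

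*SAP*

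**What the plan says.** SAP section iv (Power) adds a second power argument for the two mediation models, which it labels Hypotheses 3 and 4. It gives model fit a gating role: "Evaluation of model fit is a prerequisite for evaluating parameters within the model itself". It says that "a hypothesis of *close model fit* can be tested by assuming the Type I error rate to be 0.05", takes RMSEA of at most 0.05 as close fit and RMSEA above 0.10 as poor fit, and sets "RMSEA_{null}=0.05$, $RMSEA_{alt}=0.10".

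With N=152 it reports two results:
- df 51: "the power to detect close model fit for Hypothesis 3 is >.99"
- df 115: "the power to detect close model fit for Hypothesis 4 is .96"

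SAP section ix (Evaluation of Primary Hypotheses 3 & 4) says of the fitted model only this: "This model will be evaluated for the significance and directionality of included path coefficients and overall model fit". Neither section gives an RMSEA cut-off, a confidence-bound rule or any other criterion for deciding that fit is adequate.

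**The concern.** Power is the probability of rejecting the null. When close fit is the null, rejection is evidence that fit is not close. The printed label therefore describes the opposite of what the calculation measures. Failing to reject does not repair this, because a non-significant test is compatible with close fit and also with RMSEA values above .05.

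The SAP makes fit a prerequisite for reading the mediation paths, and mediation is listed among the primary hypotheses. Someone who reads >.99 and .96 would take it that the trial is almost certain to confirm close fit if the model is good. If the real probability is much lower, a mediation result could be reported on a model described as closely fitting when that was never shown.

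**Working it through.** **Inputs.** All are from SAP section iv except the true RMSEA values other than .10 used in steps 2 and 3. Those are assumptions, shown as a range, because the SAP gives none.
- alpha = .05; null RMSEA = .05; alternative RMSEA = .10
- df = 51 (Hypothesis 3 model) and df = 115 (Hypothesis 4 model)
- N = 152 initial, 140 retained

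**Formula.** The fit statistic is treated as noncentral chi-square with noncentrality (N − 1) × df × RMSEA².

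**Step 1: the plan's own figure, power to reject close fit when the true RMSEA is .10 (N=152).**
- df 51: noncentrality is 151 × 51 × .0025 = 19.25 under the null and 151 × 51 × .01 = 77.01 under the alternative. The 95th percentile under the null is 93.6. The chance of exceeding it under the alternative is **.965** (printed: >.99).
- df 115: noncentrality is 151 × 115 × .0025 = 43.41 and 151 × 115 × .01 = 173.65. The critical value is 192.8 and the power is **.9998** (printed: .96).

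Neither printed value is reproduced for its own model, and both are if exchanged. For df 51, using N in place of N − 1 gives .966 and alpha .10 gives .984. Power of .99 would need N=188.

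**Step 2: power to show close fit.** Showing RMSEA below .05 means rejecting RMSEA ≥ .05 in the lower tail at 5%. This is the same as requiring the upper 90% confidence bound to lie below .05. The critical value is the 5th percentile under RMSEA .05: 49.7 (df 51) and 126.8 (df 115) at N=152.

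| True RMSEA | df 51, N=152 | df 115, N=152 | df 51, N=140 | df 115, N=140 |
|---|---|---|---|---|
| 0 (exactly correct) | .475 | .787 | .428 | .731 |
| .01 | .445 | .752 | .402 | .695 |
| .03 | .244 | .428 | .224 | .388 |

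The first row is the ceiling. With a true RMSEA of .01, power of .80 would need N=265 (df 51) or N=164 (df 115).

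**Step 3: what a non-significant close-fit test would tell you (N=152).** Chance that the test of RMSEA ≤ .05 is non-significant:

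| True RMSEA | df 51 | df 115 |
|---|---|---|
| .06 | 85% | 76% |
| .07 | 64% | 39% |
| .08 | 36% | 9.5% |
| .10 | 3.5% | 0.02% |

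Non-significance is thus common just above .05 and rare at the plan's poor-fit limit. It becomes more likely with fewer infants: at true RMSEA .08 and N=140 it is 41% (df 51) and 13% (df 115).

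**The case against.** The strongest reply is that this is loose wording in a supporting paragraph. The calculation is a recognised one, and in its own direction power is high for both models whichever way the two values are assigned. Turning the test round between the plan's own limits (null .10, true RMSEA .05) also leaves power at .965 and .9998, so the trial can distinguish close from poor fit. The lower figures of .48 and .79 arise only if the whole 90% interval must lie below .05, a standard the SAP does not adopt. All of this stands. It limits the consequences, but it does not make the printed label true: the SAP claims power to detect close fit, and by its own definition close fit is RMSEA of at most .05.

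A reader might go further and infer that the SAP passes any model whose close-fit test is non-significant, and so lets mediocre models through. The documents do not support that. Neither section iv nor section ix says that non-significance counts as a pass, and the SAP defines only close and poor fit. Step 3 shows what such a rule would do if adopted. It does not describe the plan.

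A reader might also want to interpret the mediation paths whenever the upper RMSEA bound is below .10. That would be more lenient between .05 and .10 than a non-rejection rule. At true RMSEA .08 and N=152 it passes 43% of models (against 36%) for df 51 and 71% (against 9.5%) for df 115.

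**Conclusion.** The point holds as a misstatement of what was calculated. The two figures are power to reject close fit at a true RMSEA of .10, and on the printed inputs they should read about .965 (df 51) and above .99 (df 115). The power to show close fit at N=152 cannot exceed about .48 and .79, and at N=140 about .43 and .73. All four ceilings are below .80.

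These results rest on the printed df, alpha .05, the noncentral chi-square approximation, and reading close fit as an upper 90% bound below .05.

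The reach is limited. The main mediation power statement in section iv (80% at a standardized path of .237) is a separate calculation. The sample size was chosen on feasibility and resources, and the fit test as the SAP frames it still has more than .80 power. Hypotheses 1 and 2 use a separate mixed model and are unaffected.

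**What to change.** In SAP section iv:
- Relabel the two figures as the power to reject close fit when the true RMSEA is .10.
- Recompute them from the printed inputs (about .965 for df 51 and >.99 for df 115 at N=152). Relabelling the printed values as they stand would leave wrong numbers in place.
- Add that the power to show RMSEA below .05 is at most about .48 (df 51) and .79 (df 115) at N=152, and .43 and .73 at N=140, even for an exactly correct model.

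In SAP section ix, Evaluation of Primary Hypotheses 3 & 4:
- Report the RMSEA with its 90% confidence interval.
- Call fit close only if the upper bound is at most .05.
- State that a non-significant close-fit test alone is inconclusive.

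This is SAP text only and needs no extra infants, visits or data. The cost is a less favourable statement of model-fit power, and some models will have to be reported as inconclusive on closeness of fit.

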- c. problem-solving Variable: IGDI problem-solving score
- d. global development Variable: Bayley III score

Hypothesis 2: Compared to the BAU group, the START-Play group will show greater sustained improvements from pre-intervention to one year since start of intervention (long-term effect) in:

- a. sitting Variable: Gross Motor Function Measure (GMFM) sitting scores
- b. reaching Variable: Number of toy contacts
- c. problem-solving Variable: IGDI problem-solving score
- d. global development Variable: Bayley III score

Hypothesis 3 (Mediation): Improvements in global development will be (at least) partially mediated by improvements in problem-solving as a function of the intervention at the end of the project (long-term proximal effect).

Variables: GMFM scores, toy contacts, IGDI problem-solving and Bayley III scores.

SECONDARY HYPOTHESES

Analysis of moderators

1. *Hypothesis:* Severity of motor impairment will have a significant influence on overall change in IGDI problem-solving, and motor scores, as well as Bayley III scores. Variable: Severity score (see Table 1)

2. *Hypothesis:* Factors external to the child (socialization opportunities [Modified Parent Child Interaction-Dyadic Mini Code scores (Censullo, 1991) (PCI-DMC)], and home environment (HOME Inventory [Bradley, 1993] & SES), will have a moderate effect on change in GMFM, problem-solving, and Bayley III scores.

Further analysis of motor variables

3. *Hypothesis:* The START-Play group will show posture control measures that are closer to normative values than the BAU group from pre to post intervention. This hypothesis tests additional variables quantifying sitting to supplement Primary Hypothesis 1. Variables: Kinematic measures taken from video analysis.

4. *Hypothesis:* Compared to the BAU group, the START-Play Intervention group will show greater improvements in duration of toy contact and object manipulation from pre to post intervention. This hypothesis tests additional variables quantifying reaching to supplement the

Primary Hypothesis 2. Variables: Unilateral and bilateral contact number and duration, and type of contact (i.e. hand open or closed; palmar or dorsal hand surface, manipulation variables).

iii. Research Design

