over time between motor skill and cognitive skill. Testing for mediation will take place by 1.) showing that global development change is influenced by change in sitting and reaching and 2.) change in reaching and sitting are linked to problem solving, 3.) change in problem solving is linked to change in global development and 4.) the effect of change in sitting and reaching on global development is at least partially explained by change in problem solving.

Other factors which may be moderators of the final outcomes are 1) severity of neuromotor disorder, 2) health status, 3) age at entry, 4) cognition at entry. Factors external to the child which may moderate outcomes are: 1) Socioeconomic status, 2) compliance or attendance to the program visits, 3) the home environment (HOME), 4) overall amount of service provided to the child, and 5) fidelity of intervention implementation. We expect that these moderating variables will not be different between groups because of our randomization process, however tests for initial differences between groups will verify this. In addition, testing for moderation will take place after the primary research questions are addressed. Variables will be tested individually first and later in combination to account for increases in explained variability.

ix. Data Analysis: Evaluation of Specific Aims and Hypotheses

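### The SAP gives two mediation tests, one without the randomised arm, and does not say which governs; its time-order claim does not cover the motor-to-problem-solving link

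*SAP*

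**What the plan says.** **The hypothesis.** Primary Hypothesis 3 (SAP section ii, and the same in the protocol) is that gains in global development will be at least "partially mediated by improvements in problem-solving as a function of the intervention at the end of the project". It is a claim about change caused by treatment.

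**Test 1, SAP section viii (Mediating and moderating variables).** Mediation is to be tested in four steps. The first is "showing that global development change is influenced by change in sitting and reaching". The second links motor change to problem solving, and the third links problem-solving change to global-development change. The fourth is that "the effect of change in sitting and reaching on global development is at least partially explained by change in problem solving". None names the randomised arm.

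**Test 2, SAP section ix (Evaluation of Primary Hypotheses 3 & 4).** A parallel process growth model has START-Play assignment at its origin. The indirect effects are A×B and A×C1×C2, and the direct effect is D. For example: "Hypothesis 4 will be evaluated by comparing the magnitude of the $A*C_1*C_2$ indirect effect to the direct effect, D". The power section (iv) and the opening of section ix refer to this model.

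**Timing, SAP section ix.** The model assesses "possible mediating effects of improvements in sitting, reaching, and problem solving through the intervention period (RX") on "improvements in global development through the one-year follow-up (LT"). The paragraph ends: "we also meet the requirement of temporal precedence necessary for strong mediational inferences".

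**The concern.** Infants enter at 7–16 months with mild to severe impairment, and section ix itself presumes that children differ in rate of change. A child who develops quickly may gain on all three measures, whichever arm the child is in. Steps that only relate these changes to one another can then be met when START-Play has no effect. Since the SAP contains both procedures and ranks neither, an analyst could report either as prespecified, and they part company in the null case, where it matters most.

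The second issue is the sequential path. Section viii expects motor skill to lead to problem solving and then to global development. If motor and problem-solving change are both slopes over months 0–3, the data carry no time order for the first link, yet the precedence sentence makes no exception for it. The trial could then claim a motor-first mechanism that its measurement windows cannot separate from the reverse order or from a shared cause.

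**Working it through.** **1. The plan's own mediation figure.** SAP section iv gives 80% power if the mediator path is at least β = .237. A one-path Wald approximation is power = Φ(β√N − 1.96).
- N = 140: .237 × 11.83 − 1.96 = 0.84, power 0.80.
- N = 152: .237 × 12.33 − 1.96 = 0.96, power 0.83.

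The figure reproduces at the retained sample size. It belongs to the treatment-anchored model. No operating characteristic is given for the four steps.

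**2. The four steps under no treatment effect.** Inputs: N = 140 (SAP section iv) and two-sided .05 (stated there for Hypotheses 1 and 2). Each child has three standardised changes, √r·f + √(1−r)·e, where f is a shared developmental factor and e is independent noise. Treatment adds nothing. The correlation r is assumed.

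A hand calculation at r = .32:
- Steps 1 to 3, each a simple association: t = .32 × √138 / √(1 − .1024) = 3.97.
- Step 4, problem solving adjusted for motor change: partial correlation = r/(1 + r) = .242, so t = .242 × √137 / √(1 − .0588) = 2.92.
- Sobel statistic for step 4: 1/√(1/3.97² + 1/2.92²) = 2.35, above 1.96.

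A typical trial with no treatment effect therefore meets all four steps at this correlation. Section viii names no test for step 4, so two choices are simulated. The comparison requires A, C1 and C2 all to be significant with adjustment for arm, which is a simple stand-in for the section ix model.

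| Assumed r | Four steps met (Sobel) | Four steps met (adjusted path) | A, C1, C2 all met |
|---|---|---|---|
| 0 | 0% | 0% | 0.1% |
| .2 | 10% | 23–25% | 1.5–1.7% |
| .3 | 56% | 72% | 3.8% |
| .32 | 66% | 78% | 3.8% |
| .4 | 90% | 93% | 4.6% |
| .5 | 97% | 98% | 4.9–5.0% |

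The last column stays near or below 5% because path A is truly zero and is significant only at its nominal rate. Reruns put it at about 1–6% for r from .2 to .5.

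**3. Time order, link by link.**

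| Link | Windows | Time order in the plan? |
|---|---|---|
| Assignment to mediators (A) | before RX, then RX | yes |
| Mediators to global development (B, C2) | RX, then LT | yes |
| Sitting/reaching to problem solving (C1) | RX and RX | no |

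C1 is read from the sequence in section viii and from the A×C1×C2 product. The path diagram is not in the copy reviewed.

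**4. What a same-window C1 can show.** Simulation with N = 140 and assumed effects: treatment 0.8 SD, a motor/problem-solving link of 0.5 where one exists, and problem solving to global development 0.3. The motor-first chain was called supported in:
- 92% of runs when motor change came first;
- 48% when problem-solving change drove motor change;
- 84% when treatment moved both and a shared factor linked them, with no motor effect on problem solving.

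**The case against.** The strongest reply is that section ix is the analysis section, that sections iv and ix refer to the growth model, and that this model starts at assignment. Section viii names no estimator or threshold, and its lead-in concerns how motor skill relates to cognition, for which steps without treatment are natural. Most of this stands. A reader of section viii alone might infer that mediation will be analysed without a treatment term. The documents do not support that, because section ix has the term. What remains is that section viii says how mediation will be tested and nothing subordinates it to section ix.

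On timing, the precedence sentence runs from assignment to mediators in RX to outcome in LT, and the windows deliver that order. A reader might infer that the precedence claim fails altogether. It does not: A, B and C2 keep their order, and only C1 lacks one.

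On size, a reader might infer that ordinary growth is enough to pass the four steps. It is not. A common average trend gives 0%, and the children's individual rates must be correlated. The .32 in section iv is a baseline correlation, not one of slopes. The Sobel test, least squares on change scores and equal correlations are choices made for this check, not the SAP's.

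**Conclusion.** The concern holds in a limited form. The SAP has two unreconciled tests for one primary mediation hypothesis, and one can be passed with no START-Play effect. The size depends on an unstated correlation: about 10% of null trials at .2, 56% at .3 and 90% at .4 with a Sobel test, more with a less strict step 4, and none at zero. The treatment-anchored chain stays at about 1–6% for correlations of .2 to .5.

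The temporal-precedence statement is sound from RX to LT and unsupported for C1. The 48% and 84% figures rest on assumed effects and only illustrate that the direction of C1 is not identified. Neither issue touches Hypotheses 1 and 2.

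**What to change.** 1. In SAP section viii, delete the four steps, or rewrite them as paths A, C1 and C2 adjusted for treatment.
2. State that the mediation hypothesis is judged only on the section ix indirect effects that start at START-Play assignment.
3. Limit the temporal-precedence sentence to RX mediators and the LT outcome, and report C1 as a concurrent association.
4. Align the labels at the same time. Problem-solving mediation is Hypothesis 3 in section ii and Hypothesis 4 in section ix. The paths are A, B, C1, C2 and D in the text, but A, C, B1 and B2 in the figure note. The section ix text cites Figure 1, while the caption says Figure 2.

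A model that places motor change before problem-solving change could be an optional sensitivity analysis, since GMFM and IGDI are both scheduled at months 0, 2, 3 and 6. It should not replace the main model. A lag does not remove a shared growth rate, a problem-solving window running past month 3 overlaps the LT outcome period, and a shorter motor window is noisier.

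The cost is wording only, with no new visits or data. The price is a slightly weaker mechanistic claim for the sequential path.
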